#### 5.9 Efficacy Assessment

The primary efficacy assessment will be the incidence of PGD Grade 3 or greater in comparison to age and disease-matched historical controls for the UPMC Lung Transplantation program.

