## 6 Statistical Consideration

Statistical analysis for the protocol will be primarily exploratory (i.e., hypothesis generating), and no firm conclusion will be drawn based upon a confirmation oriented statistical analysis. The results will be displayed as mean±standard deviation for continuous variables, or frequency (percentage), for discrete variables. For variables with skewed distributions, both nonparametric analysis, and parametric analysis using logarithmically transformed data will be performed. The continuous efficacy variables will be analyzed by analysis of variance (ANOVA) models, which will contain terms of treatment dose, disease type, and treatment-by-disease type interaction. The treatment-by-disease type interaction will be assessed at significance level 0.10. If the treatment-by-disease type interaction is not statistically significant, the interaction effect will be removed from the model. The treatment differences will be assessed by pair-wise comparison between the study population and historical controls, using least-square means from the ANOVA model. If baseline value of each continuous efficacy variable is to be adjusted, data will be analyzed by analysis of covariance (ANCOVA).

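### Age is a matching factor for the historical controls but is absent from the analysis model, and the controls need not meet the trial's own eligibility criteria

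*Combined protocol and SAP*

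**What the plan says.** Section 5.9 (Efficacy Assessment) judges PGD incidence "in comparison to age and disease-matched historical controls for the UPMC Lung Transplantation program". It does not say whether matching is individual or by frequency, how many controls each treated patient gets, how close the ages must be, or whether the age is the recipient's or the donor's.

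Section 6 (Statistical Consideration) fits ANOVA to the continuous efficacy outcomes only, using models "which will contain terms of treatment dose, disease type, and treatment-by-disease type interaction". The treatment effect is then read from a "pair-wise comparison between the study population and historical controls", taken as a contrast of least-squares means. The only other adjustment is optional and concerns the outcome's own starting value: "If baseline value of each continuous efficacy variable is to be adjusted, data will be analyzed by analysis of covariance (ANCOVA").

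Sections 7.1.2 and 7.1.4 set the trial's exclusions. Among them are donor age above 55 years, and recipient pulmonary hypertension (idiopathic, or secondary with mean PA above 30 mm Hg). Nothing in Section 5.9 or Section 6 applies these limits to the controls. The background subsection numbered 4.3.1 names donor age and recipient pulmonary hypertension among the possible independent risk factors for PGD.

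**The concern.** The study is not randomised, so the choice of controls and the model are the only protection against confounding in the efficacy comparison. Two things weaken that protection.

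First, the investigators thought age important enough to match on, and recipients may be anywhere from 18 to 70, but age then drops out of the analysis. If matching is loose, the remaining age difference is read as treatment effect. If matching is tight, the estimate is sound, but the model does not know that age was balanced and so reports too large a standard error.

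Second, the treated group is filtered by a long list of donor and recipient exclusions, and the controls are not. Matching on age and disease does not reproduce that filter. A lower-risk treated group could be set against a less selected control group.

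**Working it through.** The plan gives no power, SD, effect size or interval, so it has no figure to reproduce.

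**1. Which matching factors reach the model**

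| Factor | Matched (5.9) | In the ANOVA (6) | In the optional ANCOVA (6) |
|---|---|---|---|
| Disease | yes | yes, with interaction | – |
| Age | yes | no | no (outcome baseline only) |
| Matched set | not stated | no | no |

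**2. Standard error when age is balanced but not modelled**

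Inputs: 8 treated (Synopsis). Assumed: 24 controls, outcome SD 1, and age explaining a share R² of the variance, from 5% to 30%.

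- SE the model aims at: √(1/8 + 1/24) = √0.1667 = 0.408.
- True SE under exact age matching: 0.408 × √(1 − R²).
- Overstatement: 1/√(1 − R²) = 1.026, 1.054, 1.118 and 1.195 at R² = 0.05, 0.10, 0.20 and 0.30.

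A simulation with close age matching (8,000 trials per value) gave these mean model SEs against the estimator's actual SD:

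| R² | Model SE | Actual SD | Ratio |
|---|---|---|---|
| 0.05 | 0.404 | 0.399 | 1.01 |
| 0.10 | 0.404 | 0.389 | 1.04 |
| 0.20 | 0.403 | 0.368 | 1.10 |
| 0.30 | 0.401 | 0.342 | 1.17 |

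The overstatement is therefore about 1-17%. It is slightly below the formula because an estimated SE averages a little low in small samples. A nominal 95% interval covered 95.4-97.3% without age and 94.8-95.2% with it.

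**3. Bias when age is not fully balanced**

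Bias in outcome SDs = (age-outcome correlation) × (mean age gap ÷ age SD). Assumed: age SD 10 years, gap 2 or 3 years.

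- Correlation 0.2: 0.2 × 2/10 = 0.04; 0.2 × 3/10 = 0.06.
- Correlation 0.5: 0.5 × 2/10 = 0.10; 0.5 × 3/10 = 0.15.

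A second simulation (3,000 trials per setting, 1 or 3 controls per patient, two disease types) agreed: 0.02-0.07 and 0.10-0.16 in absolute size with disease only, and about zero once age was added. The estimator's own sampling SD was 0.35-0.49. Matched-set terms without age gave 94-95% coverage but left the bias unchanged. At correlation 0.5, adding age narrowed the interval by 11-13% (for example 2.10 to 1.84 at 1:1, and 1.61 to 1.43 at 1:3). At 0.2 the width changed by 2% or less.

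**4. Controls outside the trial's criteria**

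Let q be the share of controls whom the trial would have excluded, with PGD rate p_x in that share and p_e in the rest. The control rate is then (1 − q)p_e + q·p_x, which exceeds p_e by q(p_x − p_e). If the excluded share carries more PGD, the control rate is raised and nitrite looks better. The documents give neither q nor p_x, so the direction can be argued but the size cannot be computed.

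**5. Whether to analyse PGD by matched set**

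With 1:1 pairs only discordant pairs count. Five in one direction give p = 2 × 0.5⁵ = 0.0625 and six give 2 × 0.5⁶ = 0.031, so at least six are needed for two-sided p < 0.05. At the local grade 2-3 rate in Table 1 (20% + 25% = 45%), 8 controls yield 8 × 0.45 = 3.6 events. Even with no events among the treated, six or more control events occur with probability 28(0.45⁶)(0.55²) + 8(0.45⁷)(0.55) + 0.45⁸ = 0.070 + 0.016 + 0.002, about 0.09.

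**The case against.** The strongest reply is that little is lost. Section 6 calls the analysis exploratory, disease type is already modelled, and with 8 treated patients a bias of 0.02-0.16 SD is small beside a sampling SD of 0.35-0.49. Matching also keeps its benefit without an age term: in the table above the actual SD falls from 0.399 to 0.342 as age matters more, and only the reported SE lags. Subsection 4.3.1 lists donor age but not recipient age as a risk factor, so the 5-30% range is an assumption. All of this stands and limits the size of the point.

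It is also fair that Section 5.9 states the matching for PGD incidence, a binary outcome, while the ANOVA covers continuous variables. But Section 6 does compare those variables with historical controls, and the documents describe no other control group. For PGD itself Section 6 offers only a summary: "The results will be displayed as mean±standard deviation for continuous variables, or frequency (percentage), for discrete variables".

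A reader might infer more than the text supports:

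- That the analysis ignores the matching. It does not, because disease type is in the model.
- That the planned confidence intervals are wrong. None is planned, and any taken from the ANOVA would be about right or mildly too wide, which is the cautious direction.
- That treated and control patients are wrongly handled as independent. This presumes individual matching; under frequency matching there are no sets to respect.
- That an age imbalance exists. No calliper or ratio is given, so it is possible but not shown.

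**Conclusion.** The point holds in a limited form. A declared matching factor, age, is missing from the declared model, and the optional ANCOVA does not bring it in. Under the stated assumptions the standard error is overstated by about 1-17%, and a 2-3 year residual age gap would shift the estimate by about 0.02-0.16 SD. With close matching that shift is near zero.

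The lack of eligibility limits on the controls may matter more, because it acts on risk factors the protocol itself names and would tend to favour nitrite. For pulmonary hypertension the direction follows from its listing as a risk factor. For donor age it rests on the inference that the cut-off at 55 marks higher-risk donors. The size is unknown. Neither issue would change how an exploratory study of 8 patients should be read, but both are cheap to settle before controls are selected.

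**What to change.** 1. Wherever historical controls are used, add age as a continuous covariate to the Section 6 ANOVA/ANCOVA beside disease type. State in Section 5.9 whether recipient or donor age is matched, whether matching is individual or by frequency, the control ratio and the age calliper. Add a matched-set term only if matching is individual, and keep age in the model with it, because sets alone do not remove age bias.
2. Draw historical controls only from UPMC lung transplant patients who meet the donor and recipient criteria of Sections 7.1.2 to 7.1.4.
3. Name the method for comparing PGD incidence. A conditional exact analysis by matched set is not recommended, because it carries little information at this size.

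Cost: one model degree of freedom for age, some record review to apply the criteria to past patients and donors, and a smaller control pool. With 1:1 matching and two disease types (both assumed), residual degrees of freedom go from 16 − 3 = 13 to 12. Terms for eight matched sets would instead use seven.

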## 7 Human subjects

#### 7.1 Subject Population

#### 7.1.1 Human subjects involvement and characteristics

Subjects of both genders and all ethnic backgrounds will be considered for inclusion in this study. Patients with end stage lung disease who are deemed eligible for placement on the lung

transplant list will be enrolled. All volunteer subjects must be at least 18 years of age and have provided informed, written consent for participation in this study. Based on the population of patients referred for lung transplantation, we expect that approximately 50% of eligible subjects will be women and 10% will be non-Caucasian. Children under 18 years of age will not be considered for inclusion in this study because children are not eligible for lung transplant at the adult lung transplant programs involved in this protocol (children are referred to a pediatric lung transplant program). If the results of this study demonstrate beneficial effects of Sodium Nitrite administration for lung transplant recipients, future studies will attempt to incorporate children through collaboration with pediatric lung transplant centers.

#### 7.1.2 Donor exclusion criteria

- Age > 55 years.
- Mechanical ventilation > 5 days prior to procurement
- Significant chest trauma or lung contusion
- Smoking history > 20 pack-year
- PaO2/FiO2 (O2 challenge) < 300
- Donor radiograph with 2 quadrant infiltrates
- Donor that are determined single lung donors prior to transplant will be excluded

#### 7.1.3 Recipient inclusion criteria

- Subjects undergoing lung transplantation.
- Subjects in the age range of 18-70 years Ability to understand and provide consent. Proxy consent will not be accepted.

#### 7.1.4 Recipient exclusion criteria

- Recipient age > 70 years.
- Recipient history of pulmonary hypertension (idiopathic PAH, or secondary PAH with mean PA > 30 mm Hg)
- Recipient history of abnormal cardiac function defined as prior CABG or LVEF < 45 %)
- Recipient history of open thoracotomy/prior pleurodesis as exclusion criteria. However
  patients who have had limited VATS procedures for biopsies would NOT be excluded
  from the study.Recipient history of cirrhosis
- Recipient history of mechanical ventilation or extracorporeal support pre-operatively

- Recipient pre-operative hypotension defined by a systolic blood pressure less than 90 mm Hg not responsive to intravenous fluids or requirement for vasoactive medications
- Recipient preoperative history of renal insufficiency, dialysis or estimated glomerular filtration rate <30 ml/min/1.73 m^2 BSA
- Patients undergoing retransplantation
- Recipient history of significant coronary artery disease that is flow limiting and unable to be corrected by further percutaneous coronary artery interventions.

#### 7.2 Recruitment and Informed Consent Procedures

Only patients with end stage lung disease deemed eligible for placement on the lung transplant list will be enrolled. All volunteer subjects must be at least 18 years of age and have provided informed, written consent for participation in this study at the time of listing for lung transplantation. The medical and surgical team will review the participation of the patient in this study at the time a decision is made for listing. Patients deemed eligible for participation will be approached by one of the study physicians for informed consent.

## 8 Potential Risks and Benefits

#### 8.1 Risk of Experimental Intervention

Sodium Nitrite: Sodium nitrite has been used commercially as a food preservative, an anticorrosive agent, a coloring agent, and an anti-anginal agent, with additional uses in laxatives, burn ointments, and liniments. Amyl nitrite has been inhaled or ingested as an euphoric stimulant. Nitrite has also been found as a contaminant in well water. Literature searches generated case reports of nausea, vomiting, abdominal pain, dizziness, headache, flushing, cyanosis, tachypnea, dyspnea, hypotension and death attributed to excess nitrite (high-dose) exposure from these sources as a consequence of methemoglobinemia due to oxidation of heme-iron in oxyhemoglobin. If levels of methemoglobin rise above approximately 30% of total hemoglobin, a subject may appear cyanotic and experience dyspnea, due to the reduced oxygen carrying capacity of hemoglobin (methemoglobin cannot bind oxygen). Levels above 50% can cause seizures, hypotension, coma and death. Note that methemoglobin levels have never risen higher than 3% at the currently used doses (30 mg) in 80 volunteers in phase I studies at the NIH. Nitrite in the form of sodium nitrite for parenteral administration is currently available and approved by the FDA for use in the emergency treatment of cyanide poisoning. Sodium Nitrite administration for this clinical indication at the labeled dosage of 300 mg causes methemoglobinemia, a desirable effect in the treatment of cyanide poisoning, as methemoglobin binds to cyanide, thus protecting cellular mitochondria. Sodium nitrite (4mg/kg, approximately 300 mg) was infused intravenously over 10 minutes in eight healthy volunteer subjects. Methemoglobin levels in venous blood samples rose from 0.02% at baseline to 5.7% of total hemoglobin following infusion of sodium nitrite, with no subject experiencing adverse events.

The sponsor of this IND application, [name], has previously held an IND for sodium nitrite (IND # 70,411) for cardiovascular applications. The cardiovascular IND involved the administration of Sodium Nitrite to 69 normal volunteers in 4 phase I-II clinical trials without observed adverse effects. We have also treated 11 subjects with sickle cell disease on this IND without observed adverse effects. The low doses of nitrite used in these investigational treatment regimens – approximately 40 mg or 13% of the dose (300mg) used in the emergency treatment of cyanide poisoning – do not produce methemoglobin levels greater than 3% and have not been associated with clinically significant hypotension. There have been no adverse events noted in the 80 treated normal human volunteers and patients with sickle cell disease. While the safety of nitrite in lung transplant recipients has not been established, the short plasma half-life (T1/2 = 42 mins ) and dose chosen for this study minimize the risk of subjects experiencing the known effects of nitrite, specifically methemoglobinemia and hypotension.

## 9 Protection against Patient Risk

#### 9.1 **Protection against General Patient Risk**

All research interventions/activities will be conducted in private room/areas. The collection of sensitive information about subjects is limited to the amount necessary to achieve the aims of the research.

All demographic and clinical information including the required and optional end points about the subject will be collected on hard copy case report forms used for data entry into a locked database. The hard copy casebooks will be maintained in the data center under the supervision

of Drs. [name] and [name]. The data will be stripped of individual identifiers and stored anonymously with a subject number. Information linking subject identifiers with the coded subject number will be stored under password protection on computers in locked areas, with access only to the database manager. Maintaining records in locked files in locked offices will protect confidentiality of subjects. Research Data are maintained on a password-protected computer that is accessible only to the database will be limited to the data manager and staff will sign confidentiality statements. Access to the database will be limited to the data manager and staff under the supervision of Drs. [name] and [name]. Blood specimens will be stripped of subject identifiers and stored according to a similar coding protocol as described above. These specimens will be stored safely in the custody of the sub-investigators responsible for the individual assays. These sub-investigators will limit future access to any remaining samples to only those investigators with prior IRB approval for their studies. For the PK assays these will be stored by [name] laboratory.

All staff involved in this study are properly credentialed and instructed in the areas of testing, confidentiality, and safety.

The Investigator will retain the data for up to 2 years following termination of this IND application. The investigator may continue to use and disclose subjects' identifiable information for the purpose of this study for a minimum of seven years after final reporting or publication of the study. If the subject and/or legal representative decide to withdraw or be withdrawn from study participation, they may request that the study data and samples be destroyed.

#### 9.2 Protection against Patient Risks Related to the Study Drug

The following components have been incorporated to protect the study subjects from risk related to the study drug:

- Small sample size consistent with the exploratory nature of the trial.
- Specific exclusion criteria to provide a stable population of patients listed for single or double lung transplant, and non-enrollment of patients listed for retransplantation with significant co-morbidities that might place them at excess risk (see exclusion criteria above).
- Continuous monitoring by an independent data and safety monitoring board.

- Involvement by expert staff with a broad range of expertise in the administration of Sodium Nitrite, and the pre and postoperative care of patients undergoing lung transplantation.
- Frequent monitoring for adverse effects of the study drug will be conducted during and following its administration.

## 10 Data and Safety Monitoring Plan

#### 10.1 Data and Safety Monitoring Board

An Independent Data and Safety Monitoring Board (IDSMB) will be established; to be comprised of individuals who are not involved with this study protocol. The DSMB will oversee patient safety in this clinical trial. The DSMB will be comprised of members including senior experts in pulmonary medicine, clinical research, clinical trial design, biostatistics, psychosocial issues relating to chronic disease, and research ethics. The Data and Safety Monitoring Board will conduct interim mentoring of accumulating data from research activities to assure the continue safety of human subjects, relevance and appropriateness of the study, and the integrity of research data.

#### 10.2 Data and Safety Monitoring Plan

Assuring patient safety is an essential component of this protocol. The study investigators have primary responsibility for subject safety monitoring. The investigators will evaluate all adverse events. The study coordinators must view patient records for possible adverse events until 72 hours after the last dose of study drug. All untoward medical occurrences observed in subjects receiving the study drug will be recorded on the participants' adverse event case report forms (CRF) by the study coordinator under the supervision of the clinical investigator. The CRF will then be reviewed for completeness and internal consistency. Subsequently, the CRFs will be recorded on an electronic password-guarded study database. In addition to internal safeguards built into a computerized system, external safeguards will be put in place to ensure that access to the computerized system and to the data is restricted to authorized personnel. Training conducted by qualified individuals on a continuing basis will be provided to individuals in the specific operations with regard to computerized systems that they are to perform during the course of the study.

The Clinical Investigator will work with the reporting sub-investigators to prepare a detailed written summary of serious, unexpected, and study drug-related adverse events, and will compare, and contrast the event with prior events. The detailed written summary will be provided to the IDSMB and also to the sponsor of the IND, [name]. Adverse events will be reported. Adverse events will be reported to IRB as per guidelines.

#### 10.3 Parameters to be Monitored

The Clinical Investigator will evaluate any changes in laboratory values and physical signs, and will determine if the change is clinically important, and different from what is expected in the clinical course of patients following a lung transplant. Expected events for lung transplant patients are untoward clinical occurrences that are perceived by the clinical investigator to occur with reasonable frequency in the day to day care of patients with a lung transplant, treated in the hospital setting. Examples of adverse events that are expected in the course of lung transplant care include infection, rejection, and organ failures. Such events will not be considered reportable adverse events unless the event is considered by the clinical investigator to be associated with the study drug or experimental procedures, or is unexpectedly severe or infrequent for a patient undergoing lung transplantation.

An event will be considered to be study drug- or experimental procedure-related if the event follows a reasonable, temporal sequence from the study drug/procedure, and could readily have been produced by the study drug/procedure. An event will be considered to be unexpected for the study drug if it is not identified as a potential adverse event in this clinical protocol, or is unexpectedly severe, or occurs more frequent than events described herein. The most common adverse events expected for this intervention would be hypotension and methemoglobinemia. These events will be reported to the Sponsor of the IND, [name] within 5 days of the event.

